APPENDIX 2. SCHEDULE OF EVENTS – POST WITHDRAWAL FOLLOW-UP

IMPORTANT NOTE: For the duration of the COVID-19 pandemic, follow the COVID-19 Modified Appendix 2-C instead (per Section 6.2).

IS Withdrawal Follow-up Weeks ¹	0	13	26	52	78	104	130	156
Visit Number ^{2,3}	201 ⁴	202	203	204	205	206	207	208
General Assessments								
Limited physical exam	X	X	X	X	X	X	X	X
Vital signs including weight	X	X	X	X	X	X	X	X
Quality of Life Questionnaires	X		X	X	X	X	X	X
Status Change since prior visit ⁵	X	X	X	X	X	X	X	X
Telephone consultation ⁶	X							X
ECG					Prior to restarting tacrolimus ⁷			
Local Clinical Laboratory Assessments								
LFTs ⁸		Every 4 weeks		Every 8 weeks			Every 12 weeks	
CBC w/differential	X	X	X	X	X	X	X	X
Comprehensive metabolic panel, includes LFTs	X	X	X	X	X	X	X	X
Liver biopsy				X				X
Mechanistic Laboratory Assessments								
Frozen PBMC collection	X		X	X		X		X
Serum collection	X		X	X		X		X
Whole blood collection	X		X	X		X		X
Urine pellet collection	X		X	X		X		X
Fecal collection ⁹	X		X	X		X		X
Liver biopsy collection				X				X

¹ The assessments outlined in Appendix 2 should be completed for all participants who initiated and successfully completed immunosuppression withdrawal. Follow-up should begin within 2 weeks of the date of completion of the participant's last taper level (see section 3.1.3).

² If a for-cause liver biopsy is needed, follow all assessments specified in Appendix 5. If the for-cause biopsy occurs within 8 weeks prior to a scheduled protocol visit, complete all clinical and mechanistic assessments listed in Appendix 5 at the time of the for-cause biopsy. The for-cause biopsy visit will take the place of the scheduled protocol visit.

³ If a participant restarts immunosuppression after successfully completing immunosuppression withdrawal, follow the assessments listed in Appendix 4. **Appendix 2 visits to be completed in addition and concurrently with Appendix 4.**

⁴ For any participant requesting early termination from the study, follow all assessments specified here, Visit 201.

⁵ Includes assessment of change in adverse events and concomitant medications. Changes should be recorded in eCRFs as appropriate.

⁶ Complete following the performance of each liver function test assessment done outside of a transplant center clinical visit; AEs and concomitant medications to be reviewed.

⁷ For participants who need to restart tacrolimus for biopsy-confirmed or presumed acute rejection (see section 6.8). A follow-up ECG will be performed within 7 days after tacrolimus has been restarted. ECG findings will be monitored per the site's standard of care until the participant is taking a stable dose of tacrolimus. Evidence of a prolonged QTc interval will be appropriately evaluated and treated.

⁸ If participant experiences a rejection episode, complete liver function tests per standard of care until resolution as determined by the investigator. Record all liver function tests performed during a rejection episode in EDC.

⁹ Participant must bring fecal sample in a specimen collection container provided at the previous protocol visit.

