the duration of the COVID-19 pandemic, Biopsy Visit 208 should be completed -4 weeks to +6 months of the scheduled time point listed in Appendix 2-C.

- If a participant needs a for-cause biopsy within 8 weeks prior to a scheduled protocol visit, complete all clinical and mechanistic assessments listed in Appendix 5 at the time of the for-cause biopsy.
 - If the scheduled protocol visit occurs during Appendix 1A, complete all clinical assessments noted for the Appendix 1A visit but do not complete any mechanistic collections.
 - If the scheduled protocol visit is listed in Appendices 2-4, the for-cause biopsy visit will take the place of the scheduled protocol visit.
- If the Appendix 4 visit occurs within 1 month (4 weeks) of a scheduled protocol Appendix 2 visit, complete the Appendix 2 visit while collecting all mechanistic samples listed in the Appendix 4 visit in lieu of completing an additional visit.

Table 4. Frequency of Liver Function Tests

Population	Timing	Frequency
For all participants who initiate immunosuppression withdrawal	During immunosuppression withdrawal	Every 3 weeks*
	≤ 26 weeks post immunosuppression withdrawal	Every 4 weeks
	26-52 weeks post immunosuppression withdrawal	Every 8 weeks
	> 52 weeks post immunosuppression withdrawal	Every 12 weeks
	During Rejection	Liver function tests after the rejection episode per standard of care until resolution as determined by the investigator
Additional assessment for participants who successfully complete immunosuppression withdrawal and then restart immunosuppression therapy	26 weeks post immunosuppression restart	Once

*Every 2 weeks between Visits 103-105.

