6.7.3 Presumed Rejection

Every effort should be made to confirm all episodes of suspected rejection with a biopsy. However in cases where this is medically contraindicated, participants may be treated empirically based on clinical suspicion. Participants with allograft dysfunction who are treated with an increase in immunosuppression without a confirmatory biopsy will be considered to have **presumed rejection**.

Participants with presumed rejection must undergo a biopsy within a week after initiation of treatment for allograft dysfunction, unless medically contraindicated. If the biopsy is negative for rejection the participants may continue with immunosuppression withdrawal. If the biopsy is positive for rejection or if the participant is unable to undergo a biopsy they will be considered to have failed immunosuppression withdrawal.

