7.6 GENE EXPRESSION

We propose to study gene expression in study participants, potentially using blood and/or PBMC (potentially whole PBMC and/or separated cell populations), urine pellet, and/or graft specimens collected prior to initiation of immunosuppression weaning. These experiments may also include DNA methylation assays using whole PBMC and/or enriched cell populations. This approach permits an unbiased assessment and avoids the confounding influences encountered when comparing already successfully weaned with those who failed weaning and remain on immunosuppression. These experiments may also be done on samples obtained during weaning, and following weaning success/failure. Comparison of pre, during, and post weaning samples in operationally tolerant patients may also be performed to determine whether any tolerance signal observed persists during and after immunosuppression discontinuation. Samples from tolerant participants may also be compared to appropriate samples from participants that have failed to be successfully withdrawn from immunosuppression during tapering (non-tolerant), and samples from participants that successfully withdrew from all immunosuppression during tapering, but were subsequently re-started on immunosuppression for clinical cause (returned to immunosuppression).

We will potentially analyze blood and/or PBMC, urine pellet, and/or liver biopsy specimens. Recent analysis of liver biopsies by microarray, followed by validation of gene changes by RT-PCR⁸ has identified a molecular signature of tolerance that requires further assessment in the more diverse US population. [name] liver tissue gene signature discriminated, with high specificity and sensitivity, at baseline those patients that could successfully withdraw immunosuppression from those that could not. This predictive signature was different from those previously reported from PBMCs or whole blood and appears more robust. Therefore, we may use Q-PCR to test for previously reported signatures in samples, as well as query for a novel signature(s) using microarray technology in samples.

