APPENDIX 3. SCHEDULE OF EVENTS – SAFETY FOLLOW-UP

IMPORTANT NOTE: For the duration of the COVID-19 pandemic, follow the COVID-19 Modified Appendix 3-C instead.

Safety Follow-up Weeks ¹	0	13	26	52	104	156
Visit Number ²	301 ^{3,4}	302	303	304	305	306
General Assessments						
Limited Physical Exam	X	X	X	X	X	X
Vital signed including weight	X	X	X	X	X	X
Quality of Life Questionnaires	X		X	X	X	X
Status Change since prior visit ⁵	X	X	X	X	X	X
Telephone consultation ⁶	X					X
ECG			Prior to restarting tacrolimus if on MMF monotherapy ⁷			
Local Clinical Laboratory Assessments						
LFTs ⁸		Every 4 weeks		Every 8 weeks		Every 12 weeks
CBC w/differential	X	X	X	X	X	X
Comprehensive metabolic panel, includes LFTs	X	X	X	X	X	X
Mechanistic Laboratory Assessments						
Frozen PBMC collection	X		X	X	X	X
Serum collection	X		X	X	X	X
Whole blood collection	X		X	X	X	X
Urine pellet collection	X		X	X	X	X
Fecal collection	X		X	X	X	X

¹ The assessments outlined in Appendix 3 should be completed for all participants who initiated but did not complete immunosuppression withdrawal. Follow-up should begin within 2 weeks of the date of immunosuppression withdrawal failure (see section 3.1.3.5).

² If a for-cause liver biopsy is needed, follow all assessments specified in Appendix 5. If the for-cause biopsy occurs within 8 weeks prior to a scheduled protocol visit, complete all clinical and mechanistic assessments listed in Appendix 5 at the time of the for-cause biopsy. The for-cause biopsy visit will take the place of the scheduled protocol visit.

³ If a for-cause liver biopsy visit took place within 8 weeks of visit 301, all mechanistic assessments listed in Appendix 5 at the time of the for-cause biopsy visit should be completed in lieu of mechanistic assessments listed for visit 301.

⁴ For any participant requesting early termination from the study, follow all assessments specified here, Visit 301.

⁵ Includes assessment of change in adverse events and concomitant medications. Changes should be recorded in eCRFs as appropriate.

⁶ Complete following the performance of each liver function test assessment done outside of a transplant center clinical visit; AEs and concomitant medications to be reviewed.

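### A for-cause biopsy late in the taper can displace the Visit 201 mechanistic collection, so that an on-drug sample stands in for the first off-drug one

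*Protocol*

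**What the plan says.** Appendix 2, footnote 2, is attached to the whole visit-number row: "If the for-cause biopsy occurs within 8 weeks prior to a scheduled protocol visit, complete all clinical and mechanistic assessments listed in Appendix 5", and then "The for-cause biopsy visit will take the place of the scheduled protocol visit". Section 6.1.1 decides by the appendix in which the visit appears, not by when the biopsy was done: "If the scheduled protocol visit is listed in Appendices 2-4, the for-cause biopsy visit will take the place of the scheduled protocol visit". Visits within the taper are treated differently: "If the scheduled protocol visit occurs during Appendix 1A, complete all clinical assessments noted for the Appendix 1A visit", with the mechanistic collections left out. Appendix 1A, footnote 2, says the same.

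Visit 201 is the first column of Appendix 2, at follow-up week 0. Footnote 1 fixes its timing: "Follow-up should begin within 2 weeks of the date of completion of the" participant's last taper level. The visit carries examination, vital signs, quality-of-life forms, blood count, metabolic panel, and PBMC, serum, whole blood, urine and fecal collection.

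Appendix 3 has a separate note for its own week-0 visit. Under footnote 3, the mechanistic assessments from a recent for-cause biopsy "should be completed in lieu of mechanistic assessments listed for visit 301", and the note does not touch the clinical part. Appendix 2 has no corresponding note for Visit 201.

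Section 6.7.3 allows a participant to go on after a for-cause biopsy: "If the biopsy is negative for rejection the participants may continue with immunosuppression withdrawal". It says this of presumed rejection. Section 7.6 foresees a use for the samples: "Comparison of pre, during, and post weaning samples in operationally tolerant patients may also be performed", to see whether a tolerance signal lasts once the drugs have stopped.

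**The concern.** The look-back from Visit 201 crosses the boundary between on-drug and off-drug time. For every later Appendix 2 visit, a for-cause biopsy up to 8 weeks earlier falls in the same phase as the visit it replaces, apart from any restart of treatment. For Visit 201 it falls mostly or wholly in the taper.

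At stake is the sample closest to complete discontinuation. A during- versus post-weaning comparison needs a sample taken soon after the last dose. For the participants concerned, the plan as written supplies one taken before the last dose and during unexplained dysfunction, and the next scheduled collection is half a year later.

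**Working it through.** **The rule as the SAP uses it.** SAP section 7.2.1 applies the 8-week replacement to Visit 204 (week 52): 52 − 8 = 44. This reproduces the SAP's 44 weeks, so the rule is meant to operate on Appendix 2 visits as written.

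**Taper length.** Section 3.1.3.1 gives 8 intervals × 3 weeks = 24 weeks. With a mycophenolate compound (section 3.1.3.3), 24 + 3 weeks of stability + 6 weeks of weaning = 33. With the 12 weeks of pauses allowed in section 3.1.3.4, 33 + 12 = 45. This matches the stated range of 24 to 45 weeks.

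**The rule applied to Visit 201.** Opening of the window = week of Visit 201 − 8.
- Visit 201 on the day the taper ends: 0 − 8 = week −8, so 8 on-drug weeks (8/3 = 2.7 taper levels).
- Visit 201 two weeks later: 2 − 8 = week −6, so 6 on-drug weeks (6/3 = 2.0 taper levels).

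**State of the participant in that window.** The medication rows of Appendix 1A mark CNI through Visit 108 (level 8) and mycophenolate through Visit 111. Section 6.6.1 requires a for-cause biopsy when unexplained dysfunction persists beyond 72 hours. The replacement sample is therefore taken on drug and during dysfunction.

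**Scheduled mechanistic collections.**
- Appendix 1A: Visits 0, 103 and 105, plus Visit 109 for participants on mycophenolate. All precede complete discontinuation.
- Appendix 2: Visits 201 (week 0), 203 (26), 204 (52), 206 (104) and 208 (156). Visit 202 (week 13) has none.

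Visit 201 is thus the only scheduled off-drug collection before week 26. If it is replaced by a biopsy at the opening of the window, the interval to the next scheduled collection is 26 + 6 = 32 to 26 + 8 = 34 weeks. If it is kept, the first off-drug sample falls at week 0 to 2, which is 26 − 2 = 24 to 26 − 0 = 26 weeks sooner.

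**Three readings of the text for Visit 201.**
- Section 6.1.1 and Appendix 2, footnote 2, taken literally: the whole visit is replaced. The week-0 quality-of-life forms go too, because Appendix 5 contains none.
- Appendix 1A, footnote 2, carried over to Visit 201: clinical part kept, mechanistic part dropped.
- Appendix 3, footnote 3, used by analogy: again only the mechanistic part is swapped.

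The off-drug mechanistic sample is lost under all three. The clinical part is lost only under the first.

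**Use in the SAP.** The eGFR and quality-of-life baselines come from Visit 0, and tolerance status rests on the week-52 biopsy (Visit 204). No clinical endpoint names Visit 201.

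**The case against.** The strongest reply is that almost nobody meets the conditions and no specified analysis suffers. Each dose reduction depends on stable liver tests over the preceding 3 weeks, and a pause moves Visit 201 further from the biopsy. Section 6.8 leaves a return to baseline immunosuppression to the investigator when the biopsy shows no rejection or is indeterminate. Dysfunction in the stability period between CNI and mycophenolate sends the participant to Appendix 3. The section 7.6 comparison is only a possibility. The example time points in section 7.6 (baseline and annually for tolerant participants) and section 7.4 (before withdrawal and years 1 and 2) do not include week 0. The SAP notes that immunosuppression is recorded daily, so the drug status of any sample can be recovered. All of this stands and keeps the point small. Daily dosing records can correct a label, but they cannot supply a sample that was never drawn.

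A reader might go further in three ways that the documents do not support.
- **A gap in liver testing at discontinuation, in conflict with Table 4.** Liver tests are a separate series in Table 4 and have their own row in Appendices 1A and 2. Section 6.1.1 gives local laboratory tests their own windows. Replacing a visit does not cancel that series.
- **A participant with recent dysfunction necessarily skips the visit.** Appendix 1A, footnote 2, can be read as keeping the clinical assessments. Appendix 2, footnote 1, wants follow-up to start after completion for everyone who completes. The text is unsettled on this.
- **A third of negative for-cause biopsies in the taper fall under the rule (8/24).** That assumes evenly spread biopsies, no pause, and Visit 201 on the last day. With Visit 201 two weeks later it is 6/24 = 25%. With one 4-week pause it is (8 − 4)/24 = 17% or (6 − 4)/24 = 8%. The documents give no rate of such biopsies, so no count of participants can be supported.

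**Conclusion.** The point holds for the mechanistic samples and is minor. As written, the replacement rule lets a for-cause biopsy visit from the last 6 to 8 weeks of the taper displace the only scheduled off-drug mechanistic collection before week 26, and it does so under each of the three readings set out above. It concerns only participants whose for-cause biopsy does not end withdrawal and who then complete the taper, probably a few. It weakens an optional comparison and leaves the primary endpoint and the SAP's clinical endpoints untouched.

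The conclusion rests on these assumptions:
- Participants are on drug through the last taper level. This is taken from the Appendix 1A medication rows, because the taper flowcharts are not shown.
- Follow-up weeks are counted from the end of the taper.
- The regular schedule is in force. Under COVID-19 Appendix 2-C, Visit 201 has no mechanistic collection and footnote 2 has no replacement wording.
- The mechanistic analysis plan, which is separate and was not available, does not already deal with these samples.

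**What to change.** Add a footnote to Appendix 2, with matching text in section 6.1.1, that a for-cause biopsy done before the last dose of immunosuppression does not replace the Visit 201 mechanistic collection. In the mechanistic analysis plan, assign the samples from such a biopsy visit to an on-taper time point. Copying the Visit 301 footnote would not be enough, since it gives up exactly the mechanistic samples that matter here.

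For the clinical assessments at Visit 201, section 6.1.1, Appendix 1A footnote 2, Appendix 2 footnotes 1 and 2, and Appendix 3 footnotes 2 and 3 must be reconciled. Which clinical rule applies is for the sponsor to settle.

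The collection is already on the schedule, so the cost is a short protocol change and one additional research draw within 8 weeks for a few participants. A week-0 sample that is not drawn cannot be obtained later.

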APPENDIX 2-C. (COVID-19 MODIFIED) SCHEDULE OF EVENTS – POST WITHDRAWAL FOLLOW-UP

IS Withdrawal Follow-up Weeks ¹	0	13	26	52	78	104	130	156
Visit Number ²	201 ³	202	203	204	205	206	207	208
General Assessments								
Limited physical exam								X
Vital signs including weight								X
Quality of Life Questionnaires ⁴				X	X	X	X	X
Status Change since prior visit								X
Telephone consultation ⁵	X							X
ECG				Prior to restarting tacrolimus ⁶				
Local Clinical Laboratory Assessments								
LFTs ⁷				Every 8 weeks		Every 12 weeks		
CBC w/differential			X	X	X	X	X	X
Comprehensive metabolic panel, includes LFTs			X	X	X	X	X	X
Liver biopsy								X
Mechanistic Laboratory Assessments								
Frozen PBMC collection								X
Serum collection								X
Whole blood collection								X
Urine pellet collection								X
Fecal collection								X
Liver biopsy collection								X

¹ The assessments outlined in Appendix 2 should be completed for all participants who initiated and successfully completed immunosuppression withdrawal. Follow-up should begin within 2 weeks of the date of completion of the participant's last taper level (see section 3.1.3).

² If a for-cause liver biopsy is needed, follow Appendix 5.

³ For any participant requesting early termination from the study, collect the following assessments if possible: telephone consultation with AE and concomitant medication update, CBC with diff, and comprehensive metabolic panel including LFTs.

⁴ Complete Quality of Life assessment by mail.

⁵ Complete following the performance of each liver function test assessment done outside of a transplant center clinical visit; AEs and concomitant medications to be reviewed.

⁶ For participants who need to restart tacrolimus for biopsy-confirmed or presumed acute rejection (see section 6.8). A follow-up ECG will be performed within 7 days after tacrolimus has been restarted. ECG findings will be monitored per the site's standard of care until the participant is taking a stable dose of tacrolimus. Evidence of a prolonged QTc interval will be appropriately evaluated and treated.

⁷ If participant experiences a rejection episode, complete liver function tests per standard of care until resolution as determined by the investigator. Record all liver function tests performed during a rejection episode in EDC.

APPENDIX 3. SCHEDULE OF EVENTS – SAFETY FOLLOW-UP

IMPORTANT NOTE: For the duration of the COVID-19 pandemic, follow the COVID-19 Modified Appendix 3-C instead.

Safety Follow-up Weeks ¹	0	13	26	52	104	156
Visit Number ²	301 ^{3,4}	302	303	304	305	306
General Assessments						
Limited Physical Exam	X	X	X	X	X	X
Vital signed including weight	X	X	X	X	X	X
Quality of Life Questionnaires	X		X	X	X	X
Status Change since prior visit ⁵	X	X	X	X	X	X
Telephone consultation ⁶	X					X
ECG			Prior to restarting tacrolimus if on MMF monotherapy ⁷			
Local Clinical Laboratory Assessments						
LFTs ⁸		Every 4 weeks		Every 8 weeks		Every 12 weeks
CBC w/differential	X	X	X	X	X	X
Comprehensive metabolic panel, includes LFTs	X	X	X	X	X	X
Mechanistic Laboratory Assessments						
Frozen PBMC collection	X		X	X	X	X
Serum collection	X		X	X	X	X
Whole blood collection	X		X	X	X	X
Urine pellet collection	X		X	X	X	X
Fecal collection	X		X	X	X	X

¹ The assessments outlined in Appendix 3 should be completed for all participants who initiated but did not complete immunosuppression withdrawal. Follow-up should begin within 2 weeks of the date of immunosuppression withdrawal failure (see section 3.1.3.5).

² If a for-cause liver biopsy is needed, follow all assessments specified in Appendix 5. If the for-cause biopsy occurs within 8 weeks prior to a scheduled protocol visit, complete all clinical and mechanistic assessments listed in Appendix 5 at the time of the for-cause biopsy. The for-cause biopsy visit will take the place of the scheduled protocol visit.

³ If a for-cause liver biopsy visit took place within 8 weeks of visit 301, all mechanistic assessments listed in Appendix 5 at the time of the for-cause biopsy visit should be completed in lieu of mechanistic assessments listed for visit 301.

⁴ For any participant requesting early termination from the study, follow all assessments specified here, Visit 301.

⁵ Includes assessment of change in adverse events and concomitant medications. Changes should be recorded in eCRFs as appropriate.

⁶ Complete following the performance of each liver function test assessment done outside of a transplant center clinical visit; AEs and concomitant medications to be reviewed.

⁷ For participants on MMF monotherapy who need to restart tacrolimus for biopsy-confirmed rejection or presumed acute rejection (see section 6.8). A follow-up ECG will be performed within 7 days after tacrolimus has been restarted. ECG findings will be monitored per the site's standard of care until the subject is taking a stable dose of tacrolimus. Evidence of a prolonged QTc interval will be appropriately evaluated and treated.

⁸ If participant experiences a rejection episode, complete liver function tests per standard of care until resolution as determined by the investigator. Record all liver function tests performed during a rejection episode in EDC.

